#### Regional Nodal/ Supraclavicular Irradiation:

For patients requiring regional nodal irradiation, the physician will determine which lymph nodes are at risk and these targeted lymph nodes will be contoured (e.g. level I, II, III, and/or supraclavicular nodes and/or internal mammary lymph nodes).

The lymph nodes will be prescribed 2.66 Gy per day x 15 fractions and administered on the same day as the whole breast or chest wall treatment. The targeted regional lymph nodes should receive at least 90% of the prescribed dose. The targeted regional lymph nodes should receive less than 105% of the prescribed dose. If these dose constraints cannot be met, the treating physician has the option of decreasing the total dose to the targeted lymph nodes per day to 2.6 Gy per day x 15 fractions.

The supraclavicular nodes may be treated with an anterior oblique photon field or opposed oblique photon fields. The internal mammary nodes may be treated with deep tangents or an en face electron field.

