#### **Primary Outcome Measure:**

- Cutaneous Toxicity Rate Cutaneous toxicity rate will be assessed by the National Cancer Institute Common Toxicity Criteria (NCI-CTC) v 3. grading scale.
- 1. Rate of 20% or greater increase in arm lymphedema (compared to baseline arm measurements) will be assessed Among breast cancer patients receiving regional nodal irradiation
- 2. Rate of Grade 3 brachial plexopathy will be assessed among breast cancer patients receiving regional nodal irradiation by RTOG and LENT/SOMA scales

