### Monitoring Plan for Severe Adverse Events:

We hypothesize that a maximum of 20% of patients might experience severe acute skin side effects defined as NCI-CTC Grade 3. This corresponds to symptoms interfering with activities of daily life. A Data Safety and Monitoring Board (DSMB) will monitor patient outcomes and suspend the protocol in the event that more than 16 of 80 patients demonstrate severe acute skin toxicity. During the study, the patients will be monitored continuously throughout the study such that if at any time during the study the upper limit of the number of patients developing Grade 3 toxicity exceed what is listed in the table below, the trial will be discontinued. With a 10% dropout rate, a total sample size of 83 patients was calculated to effectively test our hypothesis. For patients not requiring regional nodal irradiation, we will only collect adverse events related to skin toxicity, lung toxicity and heart toxicity. We will not report grade 1-2 radiation dermatitis as adverse events because most patients will at least have gr 1 dermatitis. We will keep a record of toxicity at each visit by collecting the Lent Soma evaluation of

the clinician at each visit after treatment starts. Patient reported fatigue rate will not be collected on the adverse event report, but will also be recorded at each visit

Total Patients	Upper limit of number of patients with toxicity for the trial to continue	Proportion of patients with toxicity if exceed the upper limit	Lower limit of 95% Cl	Upper Limit of 95% CI
3	<3	100%	29%	100%
4	<4	100%	40%	100%
5	<4	80%	28%	99%
6	<4	67%	22%	96%
7	<5	71%	29%	96%
8	<5	63%	24%	91%
9	<5	56%	21%	86%
10	<6	60%	26%	88%
11	<6	55%	23%	93%
12	<6	50%	21%	79%
13-50	<7	>20%	NA	

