will be monitored throughout the study such that if at any time during the study the upper limit of the number of patients receiving regional nodal irradiation developing Grade 3 brachial plexopathy or 20% or greater increase in arm lymphedema exceed the number just described or more than 20% develop grade 3 skin toxicity within the breast or chest wall, the trial will be discontinued to the patients requiring regional nodal irradiation but may remain open to patients who do not require regional nodal irradiation. For patients requiring regional nodal irradiation, we will only collect adverse events related to brachial plexopathy, lymphedema, skin toxicity, lung toxicity, heart toxicity. We will not report grade 1-2 radiation dermatitis as adverse events because most patients will at least have gr 1 dermatitis. We will keep a record of toxicity at each visit by collecting the Lent Soma evaluation of the clinician at each visit after treatment starts. Patient reported fatigue rate will not be collected on the adverse event report, but will also be recorded at each visit.

Stopping rule for monitoring 3 types of toxicities in patients Receiving Regional Nodal Irradiation.

Total Patients	Upper limit of number of patients with Grade 3 brachial plexopathy (<3%)	Upper limit of number of patients with 20% or greater increase in arm lymphedema (<15%)	Upper limit of number of patients with grade 3 skin toxicity within the breast or chest wall (<20%)
3	<2	<3	<3
4	<2	<3	<4
5	<2	<4	<4
6	<2	<4	<4
7	<2	<4	<5
8	<2	<4	<5
9	<2	<5	<5
10	<2	<5	<6
11	<2	<5	<6
12	<2	<5	<6
13-30	<2	<5	<7

(If any one of the 3 stopping rules is met, the trial stops for excessive toxicity.)

**Correlative Studies**: Blood will be analyzed for inflammatory markers (TNF-alpha, soluble sTNFR2, IL-6, IL-1ra, and CRP) to determine if they are associated with development of cutaneous toxicity. By acquiring the objective UTC measurements at 5 time points, the development and resolution of cutaneous toxicity as it relates to time may be further understood.

A description of the Feasibility:

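### The nodal cohort's skin stopping limit counts Grade 3 reactions only in the breast or chest wall, so reactions confined to nodal-field skin count only toward a pooled, less sensitive rule

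*Protocol*

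**What the plan says.** The protocol section on patients requiring regional nodal irradiation gives three triggers: brachial plexopathy, arm lymphedema and skin. The skin trigger applies if "more than 20% develop grade 3 skin toxicity within the breast or chest wall". The table column heading repeats the restriction, beginning "Upper limit of number of patients with grade 3 skin toxicity within the breast or chest wall (<20". Its limits run from fewer than 3 of 3 patients to fewer than 7 for 13 to 30 patients. Under the prose, meeting a trigger closes the study to nodal patients, while it may stay open to the others.

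The same patients are irradiated beyond the breast or chest wall. In the section on regional nodal and supraclavicular irradiation: "The supraclavicular nodes may be treated with an anterior oblique photon field or opposed oblique photon fields". For another nodal group: "The internal mammary nodes may be treated with deep tangents or an en face electron field".

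Elsewhere no skin site is named:
- Primary Outcome Measure: "Cutaneous toxicity rate will be assessed by the National Cancer Institute Common Toxicity Criteria", version 3.
- Monitoring Plan for Severe Adverse Events: the event is "severe acute skin side effects defined as NCI-CTC Grade 3", and the monitoring board is to "suspend the protocol in the event that more than 16 of 80 patients demonstrate severe acute skin toxicity".
- Adverse-event collection for nodal patients lists skin toxicity without a location.

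The SAP has no stopping rule, and its toxicity grade scale names no site.

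**The concern.** Nodal irradiation is the exposure this cohort adds. The protocol's background says that patients needing it were under-represented in the earlier hypofractionation trial, and the cohort has its own limits so that it can be closed separately. Yet none of its three limits counts a severe skin reaction that appears only in a nodal field: the skin limit excludes it by location, and the other two do not measure skin. The protocol thus has two descriptions of a Grade 3 skin event, one limited by site and one not, and gives no reason for the difference. At stake is whether an excess of severe skin toxicity caused by the nodal fields would close the cohort that receives them.

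**Working it through.** **Inputs from the protocol.** 30 evaluable nodal patients and 50 breast-only patients (Data Collection), together 80; the 20% reference rate; the nodal stopping table; the rule of more than 16 of 80.

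**Reproducing the limits.** For each n, take the smallest count whose exact (Clopper-Pearson) two-sided 95% lower bound exceeds 20%. For n = 3 to 12 this gives 3, 4, 4, 4, 5, 5, 5, 6, 6, 6, and at n = 13 it gives 7, as in the table. The flat limit of 7 up to n = 30 does not follow from that criterion, which would give 12 at n = 30. It does match more than 20% of 30: 6/30 = 20.0% and 7/30 = 23.3%. The pooled rule is consistent with the same reference: 16/80 = 20.0% and 17/80 = 21.25%.

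**What one nodal-field-only Grade 3 reaction adds.** To the nodal skin limit: 0. To the plexopathy and lymphedema limits: 0. To the count out of 80: 1.

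**Illustration on assumed rates.** Let p be the true any-site Grade 3 rate in nodal patients, and s the share of affected patients whose reaction lies only in nodal-field skin. Patients with Grade 3 reactions at both sites already count, so they are not part of s. The rate that the limit sees is p(1 − s). Take p = 25%.

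The probability that the nodal table stops by n = 30 comes from an exact binomial recursion, patient by patient, that stops at the first count reaching the tabulated limit:

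| s | Counted rate | Expected count in 30 | P(stop by 30) |
|---|---|---|---|
| 0 (all sites count) | 25% | 7.5 | 0.655 |
| 1/5 | 25% × 0.8 = 20% | 6.0 | 0.397 |
| 2/5 | 25% × 0.6 = 15% | 4.5 | 0.156 |

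A single look, P(X ≥ 7 of 30), gives almost the same values: 0.65, 0.39 and 0.15.

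**The pooled rule as a substitute.** Let X be Binomial(50, b), with b the breast-only rate, and Y be Binomial(30, 0.25). The rule triggers if X + Y ≥ 17.
- b = 10%: expected count 5 + 7.5 = 12.5; P = 0.107.
- b = 15%: expected count 7.5 + 7.5 = 15; P = 0.324.

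With 15% in all 80 patients and no nodal-field-only reactions, P = 0.084. The pooled rule therefore does respond to nodal-field reactions (0.08 to 0.32 when 10 percentage points are added in the 30), but less than an any-site nodal limit, which goes from 0.156 to 0.655 for the same change.

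**The case against.** The strongest objection is that nodal-field reactions are not ignored. A reader might infer from the nodal limit that they can never count toward stopping. The documents do not support that: the pooled rule names no site, its 80 patients include the 30 nodal patients, and skin adverse events in nodal patients are collected without a site limit. This stands, and it confines the point to the nodal-specific limit. The Monitoring Plan's own table also names no site. Its rows end at 50, which suggests that it is meant for the breast-only patients, but the text does not say so.

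Four further inferences go beyond the text:
- **That the rule was copied from the breast-only cohort by oversight.** The site phrase is absent from the general monitoring plan and appears only in the nodal rule, so a deliberate choice is possible. The boost and the 115% ceiling apply to the breast or chest wall, while nodes are held below 105%, so watching the most heavily dosed skin has some logic. No such reason is stated.
- **That the monitored count must fall below the primary-outcome count.** The primary outcome is silent on site. The primary objective speaks of radiotherapy to the breast, and the photographs are of the treated breast or chest wall, so its scope may be equally narrow.
- **That every nodal field lies on separate skin.** Internal mammary nodes may be treated with deep tangents, and no separate axillary field is described. The supraclavicular field is the clear case.
- **That a definite share of stopping power is lost.** The shares of one fifth and two fifths are chosen for illustration.

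The pooled rule is also less weak when the breast-only rate is itself high. With 20% at the breast or chest wall in all 80 patients and 10% nodal-field-only in the 30, it triggers with probability 0.74. Much of that comes from the breast-only patients: with no nodal-field-only reactions it is already 0.43.

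**Conclusion.** The point holds for the nodal-specific limit. As written, a Grade 3 reaction confined to nodal-field skin cannot contribute to closing the nodal cohort on its own. It can contribute to the pooled rule, which needs 17 events, mixes in 50 patients without nodal fields, and suspends the whole protocol.

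The size is an illustration. It assumes a 25% any-site rate in nodal patients, shares of one fifth or two fifths, breast-only rates of 10% to 15%, and independent patients. On those assumptions the nodal table's chance of stopping falls from about 0.65 to 0.40 or 0.16, against 0.11 to 0.32 for the pooled rule. If nodal-field-only Grade 3 reactions do not occur, nothing is lost. The inconsistency in the event definition does not depend on these figures. This is an inexpensive improvement to safety monitoring; it does not show that stopping is blind to nodal skin toxicity altogether.

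**What to change.** Reconcile the Primary Outcome Measure, the Monitoring Plan for Severe Adverse Events and the nodal section on which skin sites count. The nodal limit, in prose and table heading, would then use the same site-unrestricted Grade 3 skin event as the Monitoring Plan, that is, a reaction in any irradiated field. If the narrower scope is intended, the protocol should say so and give the reason. Add a site field to the toxicity form so that the breast or chest wall rate can still be reported separately.

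The numerical limits need not change, since they rest on the 20% reference that the Monitoring Plan already applies to an event with no site named. The team should confirm that 20% is also the reference it wants for the wider event in nodal patients. The cost is one phrase, one form field and a higher chance of stopping the nodal cohort. That increase depends on the unknown nodal-field-only rate and need not be small: with an assumed 15% at the breast or chest wall, adding 5% or 10% nodal-field-only raises the chance of stopping by patient 30 from 0.16 to 0.40 or 0.66.

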Information regarding disease characteristics (including stage, tumor size, grade), patient demographics (including age, race, co-morbidities, social history, body mass index), systemic treatment (including hormone therapy, systemic therapy), surgical treatment, radiation treatment, and clinical outcomes (local control, distant metastasis, survival, and treatment complications) will be collected and recorded.

Patients may also be asked to participate in a long term assessment between 1 and 10 years where they will complete the same study procedures as outlined above. Patients will be compensated \$50.00 for completing this visit.

A follow up phone survey will be taken between 18 months and 10 years after treatment. Using the same scales as in the study visits, the patients will be asked to rate their fatigue level, breast pain, how happy they are with the look of their breast and how different their radiated breast is from their non-radiated breast. They will also be asked if they are on any hormonal treatment for breast cancer and if so, the date they started. We will obtain verbal consent for this survey from patients who completed this study before the follow up phone survey was originally approved on 9/24/2013.

Assuming 10% of patients dropout, 53 patients requiring breast only radiation will be enrolled (2-3 patients per month) to yield a total of 50 patients.

An additional 33 patients requiring regional nodal irradiation and breast or chest wall radiation will be enrolled. Assuming 10% of patients dropout, 33 patients of these patients will be enrolled (2-3 patients per month) to yield a total of 30 patients receiving regional nodal irradiation and breast or chest wall radiation.

In patients undergoing regional nodal irradiation, arm measurements will be taken of the ipsilateral and contralateral upper extremity at baseline, 7 - 12 weeks, and 12 – 18 months post XRT by a licensed lymphedema therapist or study staff trained by a licensed lymphedema therapist. These patients will also be assessed for brachial plexopathy using RTOG grading toxicity, LENT/SOMA grading toxicity, and a modified version of a validated questionnaire to assess symptoms of brachial plexopathy at baseline and 7 - 12 weeks, and 12 – 18 months post XRT.[24] If a patient develops RTOG or LENT/SOMA Grade 3 toxicity, an objective measurement (MRI and/or nerve conduction studies) of brachial plexopathy will be employed.

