# Patients Requiring Regional Nodal Irradiation

Among patients requiring regional nodal irradiation, we hypothesize that <3.0% of patients will develop severe brachial plexopathy following radiation to the regional nodes defined as LENT/SOMA or RTOG Grade 3 or higher (Continuous paresthesias with incomplete motor paresis; pain medication is generally required or objective neurologic findings with paresthesia or paresis) As this toxicity occurs after radiation treatment is complete, patients will be formally assessed for brachial plexopathy at baseline and at 7-12 weeks and 12-18 months post radiation for comparison with baseline assessments. However, patients will be asked to contact [name] if symptoms of brachial plexopathy develop in between or after study visits. We also hypothesize that less than 15% of patients receiving regional nodal irradiation will develop 20% or greater increase in arm lymphedema (compared to baseline measurements) assessed at 7-12 weeks and 12-18 months post radiation. Of note, lymphedema that develops in the context of weight gain (>/=15% increase in weight) or trauma to the arm will not be attributed to the radiation treatment itself and will not be considered an event to due to the treatment. If this side effect is secondary to radiation rather than surgery, it generally occurs after radiation is complete. Lymphedema that takes place during the 3 weeks of radiation or before radiation begins will be attributed to surgery. During the study, the patients

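### The nodal stopping sentence and the nodal stopping table set different limits: one Grade 3 plexopathy in 30 patients (3.3%) stops the cohort under the sentence but not under the table.

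*Protocol*

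**What the plan says.** All of the following is in the protocol section Patients Requiring Regional Nodal Irradiation, unless another section is named.

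- **Hypotheses.** For plexopathy, "we hypothesize that <3.0% of patients will develop severe brachial plexopathy following radiation to the regional nodes". For lymphedema the hypothesised rate is below 15%.
- **Stopping sentence.** At whatever point in the study the nodal counts of plexopathy or lymphedema "exceed the number just described or more than 20% develop grade 3 skin toxicity within the breast or chest wall", nodal accrual is discontinued. Patients who do not need nodal irradiation may still be enrolled.
- **Stopping table.** Its heading is "Stopping rule for monitoring 3 types of toxicities in patients Receiving Regional Nodal Irradiation". The plexopathy column is headed "Upper limit of number of patients with Grade 3 brachial plexopathy (<3"%) and reads <2 in every row. The lymphedema column carries 15% and rises from <3 to <5. The skin column is headed "Upper limit of number of patients with grade 3 skin toxicity within the breast or chest wall (<20"%) and rises from <3 to <7.
- **Note under the table.** "If any one of the 3 stopping rules is met, the trial stops for excessive toxicity".

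For comparison, the parallel sentence under Monitoring Plan for Severe Adverse Events refers to its table outright: the trial stops if "the upper limit of the number of patients developing Grade 3 toxicity exceed what is listed in the table below".

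The Data Collection section gives the cohort size: "33 patients of these patients will be enrolled (2-3 patients per month) to yield a total of 30 patients".

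**The concern.** The stopping sentence comes before the table, and no count has been given by then. The figures it refers back to can therefore only be 3% and 15%. Read that way, the first plexopathy closes the nodal cohort, while the table keeps it open until the second.

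The skin conflict does not depend on what the sentence refers back to, because the sentence states the 20% limit itself and applies it at any point in the study.

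The table's heading and note suggest that the table is the working rule, but no sentence says that it overrides the percentages. The two texts also differ on what stops: nodal accrual in the sentence, the trial in the note.

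These limits govern primary safety outcomes. Two DSMB members, one applying the sentence and one the table, could reach opposite decisions on the same data.

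**Working it through.** **Inputs.** Percentage limits of 3%, 15% and 20%, and the table's counts, come from the nodal section. Cohort size (33 enrolled, 30 evaluable) and accrual rate (2-3 per month) come from Data Collection. An entry <k is read as *k-1 events continue, k events stop*. This follows the table in the Monitoring Plan, where <3 at 3 patients is paired with 100%, that is 3/3.

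**Step 1: can the table be reproduced from its percentages?** Take the smallest count whose exact two-sided 95% lower confidence limit exceeds the header rate.
- This reproduces every skin and lymphedema entry for 3-12 patients.
- For plexopathy it gives <2 only for 3-8 patients; from 9 patients it would stop at 3 or more.
- A one-sided limit gives <2 for 3-12 patients and fails at 13, where P(X≥2) at 3% is 0.056.
- A plain percentage rule gives <1 throughout.

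None of these rules gives <2 in the 13-30 row.

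**Step 2: stopping counts side by side.** For the sentence, the stopping count is the smallest k with k/n above the percentage. For plexopathy, 1/30 = 3.33% and 1/33 = 3.03% both exceed 3%, so k = 1 at every size in the cohort.

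| Toxicity | Sentence stops at (patients) | Table stops at (patients) | Same count |
|---|---|---|---|
| Plexopathy, 3% | 1 (3-30) | 2 (3-30) | never |
| Lymphedema, 15% | 1 (3-6), 2 (7-13), 3 (14-19), 4 (20-26), 5 (27-30) | 3 (3-4), 4 (5-8), 5 (9-30) | 27-30 |
| Skin, 20% | 1 (3-4), 2 (5-9), 3 (10-14), 4 (15-19), 5 (20-24), 6 (25-29), 7 (30) | 3 (3), 4 (4-6), 5 (7-9), 6 (10-12), 7 (13-30) | 30 |

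So the table continues at skin rates of 2/3 = 67%, 4/9 = 44% and 6/13 = 46%.

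**Step 3: plexopathy among 30 patients.** Exact binomial: P(X=1) = 30·p·(1-p)^29 and P(X≥1) = 1-(1-p)^30.

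| Assumed true rate | P(X≥1): sentence stops | P(X≥2): table stops | P(X=1): opposite actions |
|---|---|---|---|
| 1% | 0.260 | 0.036 | 0.224 |
| 2% | 0.455 | 0.121 | 0.334 |
| 3% | 0.599 | 0.227 | 0.372 |

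**Step 4: would a plexopathy be known while accrual is open?** Accrual takes 33/3 = 11 to 33/2 = 16.5 months. The lag to the 7-12 week visit is 3 weeks of treatment plus 7-12 weeks, or 2.3-3.45 months, so 22-28 of 33 patients are assessed before accrual ends. The lag to the 12-18 month visit is at least 12.7 months, so 0-7 are assessed. With 1-(1-p)^m, the chance that a first event is known in time at true rates of 1%, 2% and 3% is:
- events seen at 7-12 weeks (m = 22-28): 20-25%, 36-43%, 49-57%;
- events seen only at 12-18 months (m = 0-7): 0-7%, 0-13%, 0-19%.

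**Step 5: chance of ever crossing, with a look after each patient from 3 to 30.**

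| Toxicity | Assumed true rate | Sentence | Table |
|---|---|---|---|
| Skin | 1% | 4.0% | <0.1% |
| Skin | 5% | 21% | 0.1% |
| Skin | 10% | 44% | 2.7% |
| Skin | 20% | 82% | 40% |
| Lymphedema | 10% | 60% | 18% |
| Lymphedema | 15% | 81% | 48% |

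With looks only from 10 patients on, the skin contrast at 10% is 20% against 2.6%.

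**The case against.** The strongest reply is that the plan has two layers. The Monitoring Plan pairs a whole-cohort limit (16 of 80, which is 20%) with a table of interim counts, and the nodal section can be read in the same way. The last row partly fits: 20% of 30 is 6, so 7 stops; 15% of 30 is 4.5, so 5 stops. The percentages are introduced as hypotheses, the table is titled as the stopping rule, and its note is an operative statement. One plexopathy in 30 would also arise when almost no accrual is left to stop, and the largest skin contrasts come from applying a raw percentage from the third patient on.

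Part of this stands. The table is probably what was meant, late plexopathy has little effect on accrual, and the skin contrast shrinks when looks start later.

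The two-layer reading still does not remove the conflict. The sentence applies throughout the study, not only at the end. For plexopathy, 3% of 30 is 0.9, which must be rounded up to one allowed patient to reach <2. The 20% skin limit is written as a stopping criterion, not only as a hypothesis, and differs from the table at every size from 3 to 29. The confidence-limit origin of the early rows explains the table but is not stated in the plan.

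**Conclusion.** The concern holds: the nodal section contains two stopping rules that disagree, and it does not say which governs. At 30 patients only plexopathy is affected; lymphedema and skin conflict at smaller numbers.

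Exactly one plexopathy in 30, which leads to opposite actions, has a probability of 22-37% at true rates of 1-3%. The effect on accrual is smaller than that if events appear only at 12-18 months. Skin matters more during enrolment, because a clinician grades it from fraction 15 onward.

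The true rates are assumptions, and patients are taken as independent. The timing figures also assume even accrual, radiotherapy starting at enrolment and no dropout. The stopping-count comparison depends on none of these, only on reading <k as a stop at k. This should be corrected, because the limits are decision thresholds for primary safety outcomes.

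**What to change.** Make the table the governing rule:

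1. Reword the stopping sentence so that nodal accrual stops as soon as the number of nodal patients with Grade 3 plexopathy, with the defined lymphedema increase, or with Grade 3 skin toxicity is no longer below the limit in the table that follows.
2. Label the 3%, 15% and 20% in the column headers as hypothesised rates.
3. Change the note under the table so that nodal accrual stops, not the trial, in line with the sentence.

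The table is the better default because the literal percentages would stop the cohort at the first lymphedema or skin event among the first 3-4 patients. If the sponsor and DSMB do intend a strict 3% limit for plexopathy, that column should read <1 instead.

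The SAP describes the study as already conducted, with 75 cases, and its text does not mention the stopping rules. If accrual has closed, the sponsor should state which rule was applied.

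The cost is an edit to one sentence, the column headers and one note, with no added patients or procedures.
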